# check ph assumption
test.ph <- cox.zph(cox.regr)
ggcoxzph(test.ph)
# plot KM curve
plot(survfit(cox.regr))
km.by.treat <- survfit(SurvObj ~ intervention, data = primEndpoint,
                        conf.type = "log-log")
```

Secondary endpoints will be analysed using group mean comparisons between the intervention groups (δ) adjusted for baseline assessments and centre in analysis of covariance (ANCOVA) models. Least square group differences will be reported with 95% CIs and p-values testing the null hypothesis of no intervention effect ($H_0: \delta = 0$).

```

library(emmeans)

mod.sec <- lm(var ~ intervention + var_baseline + site,
               data = secEndpoints)
# report least square group differences
tmt.means <- emmeans(mod.sec, ~ intervention)
tmt.means
pairs(tmt.means)

```

Additionally, longitudinal assessed endpoints will be analysed using Gaussian linear models for repeated measures with intervention group, time, intervention-by-time interaction and study centre as factors and baseline score as a covariate (mixed model for repeated measurements, MMRM). The error terms are assumed to follow a multivariate normal distribution with unstructured covariance matrix. Least square group differences will be reported with 95% CIs and p-values testing the null hypothesis of no intervention effect ($H_0: \delta = 0$).

```

library(lme4)
library(car)
library(emmeans)

mod.sec <- lmer(var ~ baseline_var + intervention + time + intervention * time +
                 site + (1|Patient.Id), data = secEndpoints)
summary(mod.sec)
res <- Anova(mod.sec, type = "III", test.statistic = "F")
res
tmt.means <- emmeans(mod.sec, ~ intervention * time)
pairs(tmt.means)

```

For the Readiness to Change and the Control Preference Scale, ordinal regression with logit link (proportional odds model) will be used with intervention, study centre as covariates and for readiness to change the baseline value. The model assumption will be checked.

```

library(ordinal)
library(emmeans)

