2.7 Timing of Outcome Assessments

Data is collected over a period of 12 months, with a flexible follow-up of up to 24 months in early recruited PwMS. Several measurement time points for outcome assessment are intended. They are calculated based on the randomization date: t_1 and t_0 take place before randomization; V_1 is scheduled in month 1 (30 days after randomization), V_2 in Month 3 (+90 days), V_3 in Month 6 (+180 days), V_4 in Month 12 (+365 days). For early recruited PwMS, V_5 takes place in Month 18 and V_6 in Month 24. After reaching the primary endpoint, t_x takes place. Deviations from the ideal time point are allowed to the degree of ± 28 days. Table 2 displays the assessment of variables within these time points.

Table 2 Assessments and measurement time points

| Instrument | Measurement time points | | | | | | | | |
|-------------------------------|-------------------------|----------------|----------------|----------------|----------------|----------------|-----------------------------|-----------------------------|----------------|
| | t ₋₁ | t ₀ | V ₁ | V ₂ | V ₃ | V ₄ | V ₅ [*] | V ₆ [*] | t _x |
| Demographic Data | X | | | | | | | | |
| MRI | | X | | X | X | X | X | X | |
| Clinical visit | | X | X | X | X | X | X | X | X |
| Relapse history | | X | X | X | X | X | X | X | X |
| Immunotherapy status | | X | X | X | X | X | X | X | X |
| EDSS | | X | | | | X | | | |
| RIKNO | | | | | X | | | | |
| CPS | | | | | | | X | | X |
| Decision satisfaction | | | | | | | | | X |
| Patient activation | | X | | | | X | | | |
| Emotional coping | | X | | | | X | | | |
| Changes in empowerment | | | | | | X | | | |
| Expectancy | | | X | | | | | | |
| Readiness to change | | X | | X | | X | | | |
| HAQUAMS | | X | | | | X | | | |
| EQ-5D-5L | | X | | | X | X | X | X | |
| HADS | | X | | | | X | | | |
| GLTEQ | | X | | | | X | | | |
| BSA-F | | X | | | | X | | | |
| Questionnaire of healthy diet | | X | | X | | X | | | |
| myfood24 | | X | | | | X | | | |
| Process evaluation | X | X | X | X | X | X | X | X | |
| Health economic parameters | | X | | | X | X | X | X | |

*Only in in early recruited PwMS.

3 Statistical Principles

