3.1 Confidence intervals and p-values

All tests will be performed two-sided with 5% significance level. Confidence intervals (CI) will be reported with 95% confidence level.

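### Additional MMRM: the printed code does not fit the unstructured covariance that the text states, and its default Tukey adjustment tests same-visit arm differences at about 1% instead of 5%

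*SAP*

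**What the plan says.** SAP section 5.2 introduces the model as a supplement to the ANCOVA: "Additionally, longitudinal assessed endpoints will be analysed using Gaussian linear models for repeated measures". Arm, time, their interaction and centre are factors, and the baseline score is a covariate. On the covariance it says "The error terms are assumed to follow a multivariate normal distribution with unstructured covariance matrix", and on reporting, "Least square group differences will be reported with 95% CIs and p-values testing the null hypothesis of no intervention effect". Section 3.1 adds: "All tests will be performed two-sided with 5% significance level. Confidence intervals (CI) will be reported with 95% confidence level". No multiplicity adjustment is stated anywhere in the SAP.

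The R code below that text calls `lmer` with the terms "site + (1|Patient.Id), data = secEndpoints". It then computes "tmt.means <- emmeans(mod.sec, ~ intervention * time" (closing bracket follows) and passes the result to `pairs()`, with no grouping by visit and no `adjust` argument. It also prints a Type III Anova table.

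Table 2 in section 2.7 shows which outcomes are concerned. The diet row reads "Questionnaire of healthy diet | | X | | X | | X", that is, baseline, V2 and V4. EQ-5D-5L is collected at baseline, V3, V4, V5 and V6, and the footnote to V5 and V6 says "Only in in early recruited PwMS". Readiness to change also has two post-baseline visits, but it gets an ordinal model, as does the CPS; myfood24 has its own model. That leaves EQ-5D-5L and the diet score.

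**The concern.** An analyst cannot follow both the text and the code.

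- **Covariance.** A random intercept with independent residuals is compound symmetry: one variance for all visits and one common correlation. An unstructured matrix gives each visit its own variance and each pair its own correlation. When the visit variances differ, the random-intercept model uses a pooled standard error that is too large at one visit and too small at the other.
- **Contrasts.** The text promises the arm difference. The code puts that difference into one family with contrasts nobody asked for, such as control at month 3 against intervention at month 12, and adjusts for all of them.
- **Type III table.** It does not fill the gap. Under R's default treatment coding, the intervention row in a model with an interaction tests the arm difference at the reference (first) visit only.

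At stake is the power of this additional analysis, and a choice between two models that could be made after the results are seen.

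**Working it through.** **Inputs from the SAP.** Two-sided 5% and 95% CIs (section 3.1); time as a factor (section 5.2); two post-baseline visits for diet, and two or four for EQ-5D-5L (Table 2); target of at least 240 randomised (section 2.3).

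**Assumed, because the SAP gives no values for these outcomes.** Correlation between visits 0.5; ratio of month-12 to month-3 SD of 0.8, 1.0 or 1.25; 20% missing at month 12; an effect giving about 80% power.

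**1. The stated level.** An unadjusted contrast rejects when |z| > 1.960, so the level is 2·P(Z > 1.960) = 5.0%. This reproduces section 3.1.

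**2. The printed contrasts.** With T visits there are k = 2T cells. Tukey's critical value is q(0.95; k)/√2, where q is the studentized range quantile. For a contrast with 80% power at 5%, the expected z is 1.960 + 0.842 = 2.802, and its power under Tukey is P(Z > critical value − 2.802).

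| | 2 visits (4 cells) | 4 visits (8 cells) |
|---|---|---|
| Critical value | 2.569 (2.591 at 200 df) | 3.031 |
| Level per contrast | 1.02% | 0.24% |
| Unadjusted p = 0.05 is printed as | 0.203 | 0.509 |
| CI width, if adjusted the same way | 2.569/1.960 = 1.31 times | 3.031/1.960 = 1.55 times |
| 80% power becomes | P(Z > −0.233) = 59% | P(Z > 0.229) = 41% |

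The 8-cell column applies only if V5 and V6 of EQ-5D-5L enter the model, which the SAP does not say. Run in R on simulated data, the printed lines label their output as Tukey-adjusted for a family of 4 estimates (6 pairs) with two visits and 8 estimates (28 pairs) with four.

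**3. The random intercept alone (not what the code prints).** With complete data at two visits, the model's standard error rests on the pooled variance. For SDs of 1 and 1.25 that is (1 + 1.5625)/2 = 1.281.

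- First visit: 2·P(Z > 1.96·√1.281/1) = 2.7%.
- Second visit: 2·P(Z > 1.96·√1.281/1.25) = 7.6%.
- Equal SDs: 5%.

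**4. Both departures together.** Putting 2.569 in place of 1.96 in step 3, SD ratios from 0.8 to 1.4 give levels of 0.2% to 2.6%. The level at the more variable visit would pass 5% only when r/√((1 + r²)/2) > 2.569/1.960 = 1.311, that is, r above about 2.5.

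**5. Simulation of the month-12 contrast.** N = 240, 6 sites, 1,500 runs per setting, the SAP's fixed and random terms:

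| SD ratio | Error: printed / random intercept unadjusted / unstructured unadjusted | Power, same order |
|---|---|---|
| 0.8 | 0.5 / 2.5 / 5.2% | 43 / 71 / 79% |
| 1.0 | 1.1 / 5.2 / 5.1% | 59 / 79 / 79% |
| 1.25 | 2.2 / 8.9 / 5.0% | 69 / 84 / 79% |

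The Monte Carlo standard error at 5% is √(0.05·0.95/1500) = 0.6 percentage points.

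**6. One simulated data set (SD ratio 1.25) through the SAP's `lmer`, `Anova` and `emmeans` lines.** The month-12 arm difference had p = 0.069 as printed, against p = 0.035 from the stated unstructured model by visit. The Type III intervention row gave p = 0.896, identical to the month-3 contrast.

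**The case against.** **The code may be only a sketch.** Section 5.6 allows SAS instead of R. The `Surv()` call for the primary analysis passes an argument that the function does not accept. `pairs()` prints no confidence intervals by default, so the promised CIs need a further call anyway. The prose already states the intended test. This is fair, and it means a 1% test is what the printed lines produce, not necessarily what will be reported. But the SAP does not call the code illustrative, so the conflict remains open.

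**Two causes are being merged.** The covariance mismatch does not produce the 1%; the Tukey default does. This stands, and steps 2 and 3 of the working keep them apart.

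**Little depends on it.** The ANCOVA still compares the arms on both outcomes. It has a single two-arm contrast, so it carries no Tukey penalty, and the error here is conservative. This also stands and sets the rating.

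**The Type III point is a coding caution.** The SAP never says that row supplies the month-12 test, and it does not state the contrast coding. Agreed; it matters only because the row cannot be used to rescue the unadjusted test.

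**The simulation inputs are assumed.** True. The 1.02% and 59% in step 2 do not depend on the assumed correlation, SD ratios or missing data; the figures in steps 3 to 5 illustrate a mechanism and do not predict this trial's results.

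**Conclusion.** The concern holds, as a minor point. Text and code specify different covariance models, and the code adds a multiplicity adjustment that the text does not contain. With two post-baseline visits and time as a factor, the printed contrast runs at about 1.0% instead of 5%, and a comparison with 80% power keeps 59%. If EQ-5D-5L is modelled over four visits, the figures are 0.24% and 41%. Allowing for unequal visit SDs (assumed ratios 0.8 to 1.25), the simulated error stays between 0.5% and 2.2%, so a real month-12 difference is missed more often without an excess of false positives.

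The consequence is confined to the additional analysis of EQ-5D-5L and the diet score. The two departures need correcting together: with Tukey removed and the random intercept kept, the two-visit error rate is off 5% whenever the visit SDs differ, and in the simulation it reached 8.9%.

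**What to change.** - **Model.** Fit what the text states: `mmrm` with `us(time | Patient.Id)`, or `nlme::gls` with `corSymm` and `varIdent`. The `gls` form was run for this check; the `mmrm` calls were not, because the package was not available.
- **Fallback.** Name one for non-convergence: heterogeneous compound symmetry, `csh(time | Patient.Id)`, with robust standard errors. With two visits it is the same model as unstructured (3 parameters each), so it matters only if V5 and V6 enter (5 parameters against 10).
- **Contrasts.** Report `summary(pairs(emmeans(mod, ~ intervention | time)), infer = TRUE, adjust = 'none')` at the visits in Table 1, which are months 3 and 12 for diet. If an adjustment is wanted after all, state it and its family in the text.
- **EQ-5D-5L.** State the visit of interest and whether V5 and V6 are modelled; Table 1 gives no visit for this outcome.
- **Type III table.** Drop the main-effect row, or set sum-to-zero contrasts first.

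The cost is a few lines of code and one sentence. No new data are needed.

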1.2 Objectives and Endpoints

This study investigates the hypothesis that behavioural and web-based information on immunotherapy decision making, disease management, and lifestyle can reduce the inflammatory disease activity in MS and change patient behaviour.

Clinical endpoints are evaluated by the trial statistician, while endpoints related to health economic aspects of the trial are evaluated by the health economics team and therefore not specified in this SAP. Primary and secondary endpoints are listed in Table 1.

Table 1 Objectives and related endpoints

| | Objective | Endpoint |
|------------------|--|---|
| Primary | To determine whether the EBBC programme reduces inflammatory disease activity in MS and changes patient behaviour. | Time to a new T2-lesion or new relapse. |
| Secondary | To determine the impact of the EBBC programme on patient autonomy and empowerment. | Change in the PAM from baseline to 12 months. |
| | To determine whether the EBBC programme promotes informed decisions on immunotherapy. | Comparison of the CPS after 12 months as well as after reaching the primary endpoint. |
| | To determine the impact of the EBBC programme on quality of life. | Change in the HAQUAMS from baseline to 12 months. Change in the EQ-5D-5L. |

| | Objective | Endpoint |
|--|--|--|
| | To determine whether the EBBC programme reduces anxiety and depression. | Change in the HADS from baseline to 12 months. |
| | To determine whether the EBBC programme leads to an increase in physical activity and a healthy dietary behaviour. | Change in the Readiness to change from baseline to 12 months. Change in GLTEQ from baseline to 12 months. Change in the BSA from baseline to 12 months. Change in food group (Questionnaire of healthy diet) from baseline to month 3 and to 12 month. Change in nutrient intake (myfood24) from baseline to 12 month. |

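### In the supplementary repeated-measures code, the type III intervention row tests one reference visit under R's default contrasts, not an overall intervention effect

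*SAP*

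**What the plan says.** SAP section 5.2 gives ANCOVA as the analysis of the secondary endpoints. It then adds a repeated-measures model for endpoints assessed longitudinally, with "intervention group, time, intervention-by-time interaction and study centre as factors and baseline score as a covariate". The code fits "mod.sec <- lmer(var ~ baseline_var + intervention + time + intervention * time" together with centre and a random patient intercept, then runs and prints "res <- Anova(mod.sec, type = 'III', test.statistic = 'F". After that it calls "tmt.means <- emmeans(mod.sec, ~ intervention * time" and requests pairwise comparisons.

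On inference, the text says: "Least square group differences will be reported with 95% CIs and p-values testing the null hypothesis of no intervention effect". Section 3.1 adds: "All tests will be performed two-sided with 5% significance level". Section 5.6 names R, or alternatively SAS. No code block in section 5.2 sets a contrast option.

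Table 2 in section 2.7 schedules follow-up of the diet score at V2 (month 3) and V4 (month 12). EQ-5D-5L is followed up at V3 (month 6) and V4, and at V5 and V6 in early recruits. Table 1 lists the diet endpoint as "Change in food group (Questionnaire of healthy diet) from baseline to month 3 and to 12 month" and gives no time point for EQ-5D-5L.

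**The concern.** A type III test of a main effect in the presence of an interaction depends on how the factors are coded. It is a test of the effect averaged over visits only if the time contrasts sum to zero. R's default for unordered factors is treatment coding, under which the row labelled as the intervention effect is the arm difference at whichever visit is the reference level.

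The row is the only single-line p-value carrying the intervention label in this block, so it may well be read, or reported, as the overall test. An effect that builds up to month 12 would not show in it. A p-value that depends on an unstated level order is also not a fixed, prespecified test.

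**Working it through.** **Algebra for two visits.** Let g = 1 for the intervention arm. The model mean is b0 + bG·g + bT·t + bGT·g·t, plus the baseline and centre terms.

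- Treatment coding (t = 0 at the first visit, 1 at month 12): the arm difference is bG at the first visit and bG + bGT at month 12. The type III row tests bG = 0, which is the first visit only.
- Sum-to-zero coding (t = +1 and −1): the two differences are bG + bGT and bG − bGT, so their mean is bG. The same row now tests the visit-averaged effect.
- With two arms and two visits, the interaction row tests whether the two differences are equal under either coding.

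**Running the planned code.** The SAP gives no figure to reproduce, so its lmer, Anova and emmeans calls were run on one simulated data set. Assumptions, not from the SAP: visits V2 and V4, 4 centres, outcome SD about 1, within-patient correlation about 0.6, true difference 0 at V2 and 0.4 SD at V4. The 240 patients are the target in section 2.3.

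| Coding | Intervention row, p | Contrast it matches |
|---|---|---|
| Default, V2 as reference | 0.9134 | Arm difference at V2 (p = 0.9134) |
| Default, V4 as reference | 0.131 | Arm difference at V4 (p = 0.1310) |
| Sum-to-zero | 0.4023 | Visit-averaged difference (p = 0.4023) |

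The data and the fitted model are the same in all three rows. The interaction p-value was 0.1398 each time. The emmeans comparisons were identical under default and sum-to-zero coding.

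Over 1000 simulated data sets of this kind, the intervention row rejected in 5.3% with default coding and in 51.6% with sum-to-zero coding.

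**Size by hand.** Assumptions: 240 × (1 − 0.20) = 192 analysed patients, 96 per arm; SD 1; correlation 0.5 between two visits; difference 0 at the first visit and 0.4 SD at month 12; two-sided 5%.

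- SE at one visit: √(2/96) = 0.144. SE of the two-visit average: 0.144 × √((1 + 0.5)/2) = 0.125.
- Row with the first visit as reference: true value 0, so it rejects in 5%.
- Visit-averaged test: 0.2/0.125 = 1.60, and Φ(1.60 − 1.96) = 0.36.
- Month-12 contrast: 0.4/0.144 = 2.77, and Φ(2.77 − 1.96) = 0.79.

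The 36% here and the 51.6% above differ because the simulation has more patients, a different correlation and a baseline score that explains part of the variance. The size is therefore driven by assumptions; the mechanism is not.

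**The case against.** The strongest reply is that the SAP does not declare this row to be its test. It attaches the null of no intervention effect to the least square group differences. In the code these come from emmeans, which does not depend on contrast coding. That stands. A reader might infer that the test of the stated null is itself wrong; the text does not support this. It remains true that the pairwise call does not supply one test of δ. For two visits it returns six cell comparisons with Tukey adjustment, and in the run above the V4 arm difference moved from p = 0.131 to 0.4306. The SAP does not say which comparison is δ.

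Three further inferences go too far:

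- **That a first-visit difference is of no interest.** For the diet score, change to month 3 is listed in Table 1. If the row rejects because of a month-3 difference, it has detected a listed endpoint; only its label misleads.
- **That the row could be an extrapolation to month 0.** This would need time entered as a number, and the text lists time among the factors.
- **That the rates of 5%, 36% and 79% show a loss of power in one planned test.** They belong to three different hypotheses under invented effect patterns.

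Reach is narrow. By Table 2, HAQUAMS (the key secondary endpoint), PAM, HADS, GLTEQ and BSA-F each have a single follow-up at month 12. Readiness to change is repeated but is analysed by ordinal regression. EQ-5D-5L and the diet score remain, in a model that supplements the ANCOVA.

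The point also rests on what the SAP leaves unsaid. A contrast option set elsewhere, time stored as an ordered factor (for which R's default contrasts do sum to zero), or a run in SAS would remove the fault. The SAP states none of these for the printed code.

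**Conclusion.** The point holds as a confined coding fault. Run as printed with R's defaults, the type III intervention row is a test at one reference visit, and it changes with level order. It is month 3 for the diet score and month 6 for EQ-5D-5L only if the levels are chronological.

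The consequence is a mislabelled row in a supplementary table, mainly for two endpoints, and not an error in the main inference. The rejection rates are illustrations under assumed effects, SD and correlation. A correction is still warranted, because a p-value labelled as the intervention effect should not depend on an unstated coding choice.

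**What to change.** Choose one of two changes and say in the text of section 5.2 which result is the reported test:

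1. Declare time a factor and set `options(contrasts = c('contr.sum', 'contr.poly'))` before `lmer()`. The row then tests the visit-averaged effect. State which visits enter, because this average weights every included visit equally, including V5 and V6 if those EQ-5D-5L records are used.
2. Delete the Anova line and take the p-value for δ = 0 from the arm contrast at each prespecified visit, with `pairs(emmeans(mod.sec, ~ intervention | time))` and month 12 as the main time point.

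The second fits the 12-month focus of Table 1 better and also replaces the list of all cell comparisons. The visit average would itself find the late effect in the illustration in only about 36%. Either change costs one line of code and about half a sentence of text, with no effect on data collection or sample size.

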# Ordinal regression for the Readiness to Change
mod.sec <- clm(var_RTC ~ baseline_RTC + intervention + site, link = 'logit',
                 data = secEndpoints)
summary(mod.sec)
# Predicted marginal response probabilities stratified for baseline
emmeans(mod.sec, ~ var_RTC | intervention / baseline_RTC, mode = 'prob')

# Ordinal regression for the Control Preference Scale
mod.sec <- clm(cps ~ intervention + site, link = 'logit',
                 data = secEndpoints)
summary(mod.sec)

emmeans(mod.sec, ~ cps | intervention, mode = 'prob')

# Check model assumptions
nominal_test(mod.sec) # test partial proportional odds assumption
scale_test(mod.sec) # test for signs of scale effects

```

Data obtained through myfood24 will be used to analyse intake of selected nutrients of interest comparing mean changes in intake from baseline with post intervention between IG and CG, adjusting for baseline intake.

```

library(lme4)
library(emmeans)

mod.sec.food <- lmer(var_food ~ food_baseline + intervention + (1|Patient.Id),
                      data = secEndpoints)
